3.3.4 Website analytics

Engagement and intervention usage will be assessed through website analytics. Reports on webtraffic, frequency and duration of visits will be available via secure download directly from the SWiM online platform. Access will be limited to authorised members of the research team.

3.3.5 Referral data

Aggregate/ anonymised data on number, demographic characteristics, and weight loss of the invited population will be requested from participating service providers. Participants will be asked to consent to the service provider providing data on their attendance and weight loss during the initial weight loss programme.

3.4 Randomisation

Participants will be allocated to one of the two intervention arms in a 1:1 allocation using block randomisation (block size 6) stratified by weight loss programme (Tier 2 weight management programme / Tier 3 weight management / NHS Diabetes Prevention Programme / NHS Digital Weight Management Programme / NHS Diabetes Remission Programme) and weight loss medication use (<3 months over the past 6 months, ≥ 3 months over the past 6 months, no weight loss medication use over the past 6 months). Randomisation lists will be generated by the trial statistician using Stata statistical software and incorporated into the study database by the data manager. The randomisation lists will be unknown to all other personnel, including study coordinators, outcome assessors and investigators.

Once eligibility is confirmed and the online baseline assessment is complete, participants will provide their baseline weight before being randomised during a call with the study coordination

team. The study coordinator team will inform participants of their group allocation during the call, and intervention materials will be provided accordingly.

For logistical reasons the study coordinator and the data manager will not be blinded to the allocation group. The trial statistician and investigators will be blinded to intervention allocation until the database is locked and the primary analysis complete.

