	 What are the barriers and facilitators to engagement with SWiM, and how do they vary across demographic and socioeconomic groups? What is the cost-effectiveness of SWiM compared to standard care in maintaining weight loss and preventing type 2 diabetes and other obesity-related complications?
	 How can SWiM be adapted for people using GLP1-RA pharmacotherapy or bariatric surgery to support long-term weight maintenance?
Summary of study procedures	This is a randomised, single-blinded, parallel-group trial with 1:1 allocation to the SWiM intervention or standard care.
	 Recruitment: Participants who have completed a behavioural weight management programme within six months will be identified and enrolled. Randomisation: Stratified by weight loss programme and weight
	 loss medication use. Intervention: The SWiM group will access a web-based self-help programme with behavioural exercises and telephone coaching. A paper workbook will also be available.
	 Control: Standard care with no additional structured support. Assessments: Conducted remotely at baseline, 6, 12, and 24 months, measuring weight, glycaemic control, mental health, eating behaviours, and quality of life.
	 Process evaluation and economic analysis: A mixed-methods evaluation, including participant interviews, to assess engagement, feasibility, and cost-effectiveness. Follow-up: Two years to assess long-term weight maintenance, with
	Tollow-up. Two years to assess long-term weight maintenance, with

[figure not shown]
potential health record linkage for future outcomes.

STUDY FLOW CHART

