3. METHODS

3.1 Study design

This is a pragmatic, randomised, single-blinded, parallel group trial with 1:1 randomisation. Participants will be randomised to either the acceptance-based weight maintenance programme (SWiM) or to standard care using a computer-generated sequence with 1:1 allocation stratified by weight loss programme and weight loss medication usage. Participants will complete assessments at baseline, 6, 12 and 24 months using remote measures.

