	Weight management questionnaire	Use of weight loss medications and other weight management programmes/activities used in addition to the allocated interventions	0m; 6m; 12m; 24m

Demographics	Bespoke	0m
	demographics	
	questionnaire based	
	on Progress-Plus	
	criteria (place of	
	residency,	
	race/ethnicity,	
	occupation,	
	gender/sex, religion,	
	education,	
	socioeconomic status,	
	social capital, age,	
	disability, relationship	
	status, caring	
	responsibilities, car	
	ownership, access to	
	the internet). ²⁵	

The study coordinator will send email or phone reminders to participants if a completed questionnaire is not received within seven days.

Participants will provide consent for future follow-up through routine data sources and national registries. NHS numbers will be obtained to facilitate this process.

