5. STATISTICS AND QUANTITATIVE DATA ANALYSIS

5.1 Sample Size

Previous meta-analyses suggest weight gain prevention interventions achieve effects of ~1.5kg at 12 months (less weight gain compared with controls). Our feasibility trial observed a -3.86kg (95%CI: -7.83 to 0.11kg, p=0.06) difference in weight at 6 months between SWiM participants and standard care, with SWiM participants losing ~2.2kg whereas standard care participants gained ~2.2 kg. Our expert elicitation workshop identified a potential mean difference of -1.96kg at 12 months with considerable uncertainty. Pre-trial modelling suggests interventions achieving these differences in weight regain after weight loss, and potentially even smaller differences, should be cost-effective. Thus, we designed the trial to detect a small overall effect size of ~1kg.

With 1,840 participants there is 90% power to detect a 1.01 kg difference in mean weight between SWiM and standard care as significant at the 2-sided 5% level, assuming a standard deviation at baseline of 22 kg, a 0.967 correlation between baseline and follow up 46 and 30% attrition. The correlation between baseline and follow up is based on the SWiM feasibility study, and is corroborated by data from our previous studies including weight change in the first year after finishing a weight loss programme in the WRAP trial (r=0.96) and 9 month weight change in Fenland COVID (N=1162 adults with overweight/obesity, r=0.972).

Designing the trial to detect a small weight difference in the overall sample should also allow a reasonable level of power to detect differences between SWiM and control within each WLP group (e.g. among only those who lost weight with a tier 3 programme), or within specific demographic groups (e.g. among men). Assuming approximately 368 participants from each WLP, there would be 80% power to detect a 1.96kg difference as significant at the 5% level between SWiM and standard care within each WLP.

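### The medication strata do not separate current from stopped users and the stated primary model has no medication term, so balance on current use is left to chance and its effect stays in the residual

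*Protocol*

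**What the plan says.** Section 3.4 sets three medication levels, "<3 months over the past 6 months, ≥ 3 months over the past 6 months" and no use in that window, crossed with five WLPs, which gives 15 strata. Allocation is "1:1 allocation using block randomisation (block size 6"). Section 3.1 says only that allocation is "stratified by weight loss programme and weight loss medication usage". Neither section has a level for use on the day of randomisation, and the eligibility criteria in Section 3.2 exclude neither current nor former users.

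The primary outcome (Section 3.5.1) is the change in weight from baseline to 12 months. The primary model in Section 5.2 is a mixed model on the 0, 6 and 12-month weights. Its fixed effects are timepoint, arm by timepoint, gender and WLP. The medication stratifier is not among them.

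Table 2 in Section 3.3.3 lists a weight management questionnaire at 0, 6, 12 and 24 months that covers "Use of weight loss medications and other weight management programmes/activities used in addition to the allocated interventions". Its items are not shown.

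**The concern.** Months of use over a six-month window do not tell us whether the person is still taking the drug. Someone who started two months ago and continues falls in the lowest-use stratum with someone who took it for two months and stopped four months ago. Six months of continuing use and three months of use that ended three months ago share the higher stratum. In a weight maintenance trial these people may be expected to move differently over the next year. The protocol's Background cites, for weight regain, a study whose title concerns regain after withdrawal of semaglutide, so the issue is within its own frame of reference.

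By stratifying on medication, the design already treats it as prognostic. The strata do not force balance on current versus stopped use, and the stated model has no term that would recover it. What is at stake is precision, and the protection of the 12-month contrast from a chance imbalance.

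**Working it through.** **The protocol's own figure.** Inputs from Section 5.1: N = 1,840, baseline SD 22 kg, correlation 0.967, attrition 30%, two-sided 5%.

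- Residual SD = 22 × √(1 − 0.967²) = 5.605 kg; variance 31.4 kg².
- Analysed per arm = 1,840 × 0.7 / 2 = 644.
- Standard error = 5.605 × √(2/644) = 0.312 kg.
- Power for 1.01 kg = Φ(1.01/0.312 − 1.96) = 89.9%. The protocol states: "With 1,840 participants there is 90% power to detect a 1.01 kg difference in mean weight". The figure reproduces.

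The SD of a plain change score would be 22 × √(2 × 0.033) = 5.652 kg, so the choice between change score and ANCOVA hardly affects what follows.

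**Assumed inputs.** The protocol gives none of these. Let m be the share of the sample with medication use in the past 6 months, q the share of those users who have stopped, and D the difference in mean 12-month change between stopped and current users. Take m = 20%, q = 50% and D = 5 to 8 kg, with 5 kg as the middle case. Wider ranges follow below.

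**Chance shift in the treatment effect.** The strata hold the number of users close to equal between arms, so only the stopped share among users is free to vary. With n × m = 644 × 0.2 = 128.8 users per arm:

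- SD of the between-arm difference in stopped share = √(2q(1 − q)/(nm)) = √(0.5/128.8) = 0.0623.
- SD of the shift = D × m × 0.0623 = 0.062 kg at D = 5 and 0.100 kg at D = 8.

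This takes q to be the same in both duration strata. If it differs between them, the existing strata already balance part of current status and the shift is smaller.

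**Share of the residual variance.** The variance carried by current status is m × q(1 − q) × D²: 0.2 × 0.25 × 25 = 1.25 kg² (4.0% of 31.4) at D = 5, and 3.2 kg² (10.2%) at D = 8.

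**Power for 1.01 kg.**

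| D | Adjusted for, variance inside the planned SD | Unadjusted, variance on top of the planned SD |
|---|---|---|
| 5 kg | 91.0% | 88.7% |
| 8 kg | 92.7% | 86.9% |

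If the variance is inside the planned SD and is not adjusted for, power stays at 89.9%.

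**Wider range.** With users at 10 to 50%, stopped share 30 to 50% and D = 3 to 8 kg, the SD of the chance shift runs from 0.02 to 0.16 kg. Power after adjustment, with the variance inside the planned SD, runs from 90.0% to 96.3%.

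**Within one WLP.** Section 5.1 also gives power within each WLP, with about 368 × 0.7 / 2 = 128.8 analysed per arm. At m = 20%, q = 50% and D = 8 kg the shift has SD 8 × 0.2 × √(0.5/25.76) = 0.22 kg, against a standard error of 5.605 × √(2/128.8) = 0.70 kg. The ratio is the same as overall; the absolute size is larger.

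**The case against.** The strongest reply is that nothing here is wrong or contradictory. Section 3.4 is specific, and Section 3.1 agrees with it. Randomisation balances current use in expectation in every stratum, and any chance imbalance is ordinary sampling variation that the confidence interval covers. This stands, and it limits the point to precision.

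Three stronger readings are tempting, and the protocol does not support them.

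- A reader might infer that the stratifier fails to balance what drives 12-month weight. It does balance users against non-users, and longer against shorter use. The protocol has no data showing that current status outweighs these.
- A reader might infer that the strata bring power down to about 87%. That figure (86.9% above) comes from adding 3.2 kg² to the planned residual variance at the top of the assumed gap. Redefining a stratifier that the model omits would leave the model's residual variance essentially unchanged. Only adjustment recovers it, and if the variance is already inside the planned SD there is no loss from 89.9%.
- A reader might infer that results by medication stratum would mislead about current users. No such analysis is planned: Sections 2.2 and 5.2 name WLP, PROGRESS-Plus characteristics and prior weight loss as moderators. The Study Summary does ask "How can SWiM be adapted for people using GLP1-RA pharmacotherapy or bariatric surgery to support long-term weight maintenance", but Section 3.2 excludes people with previous or planned bariatric surgery, so that question was not written to be answered from these strata.

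It is also fair to say that strata based on current use would be another imperfect proxy. They would pool new starters with long-term users, whom the duration cut largely separates, and status on day 0 is not status over the year.

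Finally, covariate detail can be left to the analysis plan. But Section 5.2 already lists the fixed effects of the primary model and includes no medication term, so the listed model is what needs changing.

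**Conclusion.** The point holds as a modest matter of precision. The strata count months of use and do not distinguish current from stopped users, and the stated primary model contains neither current status nor the medication stratifier. Balance on current use is therefore left to chance, and its effect on weight change remains in the residual.

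There is no systematic bias, and the sample size calculation is unaffected. The chance shift of 0.06 to 0.10 kg is about a fifth to a third of the 0.31 kg standard error (0.062/0.312 = 0.20; 0.100/0.312 = 0.32). The gain from adjustment is about one percentage point of power in the middle case. The share of users, the share stopped and the kilogram difference are all assumptions. The first two can be checked against baseline data pooled over arms.

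**What to change.** Keep the randomisation lists as they are. Then:

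1. Confirm that the 0-month weight management questionnaire distinguishes use at baseline from use that has stopped within the past 6 months. If it does not, add one item.
2. Add baseline medication status (current, stopped within 6 months, none) to the primary model in Section 5.2, together with its interaction with timepoint. Baseline weight is one of the modelled outcomes, so a main effect alone would shift the level at every timepoint and would not act on the change.
3. Add the medication stratification factor alongside it, and carry the same specification into the statistical analysis plan.

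Cost: one baseline item to confirm and a few parameters. The no-use level is common to both factors, so together they add three contrasts. With three timepoints that is at most nine parameters, against 2 × 644 = 1,288 participants analysed.

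Redefining the strata as current, stopped or none is optional. It keeps 5 × 3 = 15 strata but gives up forced balance on duration of use. Splitting both duration levels by current status would keep both, at 5 × 5 = 25 strata. Neither is needed for the gain described here.

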3.5 Outcomes

3.5.1 **Primary Outcome**

12-month change from baseline in weight (kg)

3.5.2 **Secondary Outcomes**

- 6 and 24-month change from baseline in weight (kg)
- 6, 12 and 24-month change from baseline in HbA1c, emotional eating, binge eating, psychological flexibility, anxiety symptoms, depression symptoms, wellbeing, physical activity, diet, sleep quality (all outcomes outlined in Table 2).

3.5.3 Health Economic Outcomes

- Health-resource use over 12 months
- Self-reported out-of-pocket costs and loss of productivity.
- Quality-adjusted life-years (QALYs) based on HRQoL (EQ-5D-5L)
- Work productivity
- Total and incremental costs from NHS and UK society perspectives; incremental net (monetary) benefit; value of information estimates.

4. PLANNED INTERVENTION AND CONTROL

4.1 Supporting Weight Management (SWiM) programme

SWiM (Supporting Weight Management) is a guided self-help programme that uses acceptance-based strategies to support weight maintenance following weight loss. It aims to help people who have lost weight reflect on what has worked (and not worked) in the past, build on what works for them, and learn new strategies to overcome challenges that typically derail weight loss maintenance.

The intervention includes access to an online web platform with 14 modules (SWiM sessions) consisting of psychoeducational content, reflective exercises, and behavioural experiments. Participants will also be provided with the option to receive an adapted paper-based workbook version of the module content. Content is described in Table 3.

SWiM is intended to be a 4-month intervention, with weekly sessions for the first 3 months followed by a one-month break, and a final module at week 17. Participants are encouraged to weigh themselves weekly and to record their weight at the start of each session. Between sessions, participants are asked to complete additional reflective exercises and behavioural experiments as 'SWiM Practice'.

To guide them through the programme, participants receive 4 telephone support calls from a "SWiM coach" over the 4-month programme. Calls are scheduled for week 1 (activation call), week 3, week 8, and week 17. There will also be 3 optional calls that can be used at any time should the participant need additional coach support or be struggling with the intervention.

The coach's role is to help the participant take ownership of their weight management, and the calls are scripted and manualised. Automated email reminders are sent to participants to remind them to complete sessions and calls. If participants are identified as at risk of disengagement (i.e., they have not attended or rescheduled their coach call), the coach will make up to 3 additional re-engagement calls.

Table 3. SWiM Intervention Outline and Content

Week	SWiM Session	Coach support	
1	Welcome to SWiM		
1	Session 1: Planning and Tracking	30-minute scheduled telephone call following completion of SWiM Session 1	
2	Session 2: Control and Acceptance		
3	Session 3: Being Willing	30-minute scheduled telephone call following completion of SWiM Session 3	
4	Session 4: Overcoming Obstacles		
5	Session 5: Being Active and Willing		
6	Session 6: Emotional Eating		
7	Session 7: Stress Management		
8	Session 8: Forming Helpful Habits	30-minute scheduled telephone call following completion of SWiM Session 8	
9	Session 9: Breaking Unhelpful Habits		
10	Session 10: Urges and Cravings		
11	Session 11: The Power of Sleep		
12	Session 12: Friends and Family		
13	Session 13: Weight Stigma and Body Image		
[4-week break to practice skills]			

		30-minute scheduled telephone call
17	Session 14: Lapses and motivation	following completion of SWiM Session
.,		14.

Web Platform

On the SWiM web platform, intervention content is divided into SWiM sessions, which are each divided into activities. Progress through the sessions is presented as a 'journey' using a map-like graphic. Star icons "light up" when activities/sessions are completed (Figure 2). As participants complete core skills exercises, these are stored in "SWiM Tools," where they can be accessed without revisiting specific sessions.

The web platform is designed to allow participants to revisit past sessions and skills, and it is intended that future rollout would include indefinite access to the website.

Figure 1: Screenshot of participant 'journey' page of SWiM website

The web platform includes a weight tracker, which tracks weight over time, displayed in a visual graphic. The weight tracker generates a line graph that automatically updates as data is entered by the participant.

As part of the first session, participants are asked to enter their prior weight loss so they can see what they have already achieved. The weight tracker automatically sets a weight maintenance target range with a boundary of ± 3 kg, which they are encouraged to stick within. This boundary can be adjusted if required as weight changes over time.

Each session starts with a reflection on the previous session and SWiM practice and the entry of weight data into the tracker. Participants will be given the option of a printed booklet of the website exercises if they prefer to write their answers down rather than enter the information

SWiM 2.0 Study Protocol ISRCTNxxxxxxx

online. The "SWiM Tools" and a weight tracker graph will be included at the back of the workbook.

4.2 Control Intervention

No additional structured support will be offered, but participants will be free to use Local Authority- or NHS-commissioned services offered as standard care or self-fund their own methods. Data on this will be captured at all time points so that we can describe the frequency and nature of weight management behaviours in this cohort by intervention type, weight loss programme, and demographics.

5. STATISTICS AND QUANTITATIVE DATA ANALYSIS

5.1 Sample Size

Previous meta-analyses suggest weight gain prevention interventions achieve effects of ~1.5kg at 12 months (less weight gain compared with controls). Our feasibility trial observed a -3.86kg (95%CI: -7.83 to 0.11kg, p=0.06) difference in weight at 6 months between SWiM participants and standard care, with SWiM participants losing ~2.2kg whereas standard care participants gained ~2.2 kg. Our expert elicitation workshop identified a potential mean difference of -1.96kg at 12 months with considerable uncertainty. Pre-trial modelling suggests interventions achieving these differences in weight regain after weight loss, and potentially even smaller differences, should be cost-effective. Thus, we designed the trial to detect a small overall effect size of ~1kg.

With 1,840 participants there is 90% power to detect a 1.01 kg difference in mean weight between SWiM and standard care as significant at the 2-sided 5% level, assuming a standard deviation at baseline of 22 kg, a 0.967 correlation between baseline and follow up 46 and 30% attrition. The correlation between baseline and follow up is based on the SWiM feasibility study, and is corroborated by data from our previous studies including weight change in the first year after finishing a weight loss programme in the WRAP trial (r=0.96) and 9 month weight change in Fenland COVID (N=1162 adults with overweight/obesity, r=0.972).

Designing the trial to detect a small weight difference in the overall sample should also allow a reasonable level of power to detect differences between SWiM and control within each WLP group (e.g. among only those who lost weight with a tier 3 programme), or within specific demographic groups (e.g. among men). Assuming approximately 368 participants from each WLP, there would be 80% power to detect a 1.96kg difference as significant at the 5% level between SWiM and standard care within each WLP.

5.2 Analysis Plan

A detailed statistical analysis plan will be developed, signed off by the Trial Steering Committee and uploaded to the ISRCTN registry prior to analysis. The intervention effect on 12-month weight change will be estimated from a 2-level mixed effects model, using weight measurements at baseline, 6 and 12 months. The model will include timepoint, intervention-by-timepoint interaction, gender and WLP as fixed effects and random intercepts to allow for repeated measures. This model assumes missing outcome data are missing at random. The primary analysis will include all available data; in a sensitivity analysis, we will impute missing values of the outcome using multiple imputation by chained equations.

Similar analyses will be performed for secondary outcomes. We aim to analyse and publish findings as soon as 12-month follow-up is complete to ensure timely communication of findings and enable analyses of inequalities in engagement and effectiveness and other determinants that we can use to understand adaptations needed; therefore 24-month values are not included in the primary analysis but will be analysed and published separately.

The primary analysis will be repeated to identify potential interactions between the intervention effect and WLP by including a three-way interaction (trial intervention x WLP x timepoint). The 12month intervention effect and 95%CI will be estimated within each WLP. Similar methods will be used to identify potential inequalities by PROGRESS Plus criteria²⁵.

Cost-effectiveness analysis

A detailed Health Economics and Modelling analysis plan (HEDMAP) will be developed and signed off by the Trial Steering Committee. The intervention effect on health-related quality of life will be estimated from a mixed effect model EQ-5D measurements taken at 0, 6 and 12 months.

The intervention effect on health care costs, out of pocket weight management services and work productivity at 12 months will be estimated from a mixed-effects model using measurements taken at 0, 6 and 12 months. Unit costs for health care services will be derived from nationally representative data sources such as the Unit Costs of Health and Social Care Programme⁵⁰ and drug tariffs.⁵¹ Total health care costs will be estimated by aggregating the health care and NHS prescribed medications used valued at their unit prices. Scores for absenteeism (work time missed), presenteeism (work impairment), work productivity loss and activity impairment will be calculated using the WPAI scoring system.

Long-term cost-effectiveness analysis will use modelling methods to extrapolate the effectiveness of the intervention on weight and other cardiometabolic risk factors at 12 and 24 months to predict long-term impacts on health and health related costs. Intervention effects on cardiometabolic risks beyond 24 months will be based on existing evidence. The relationships between cardiometabolic risks and obesity related complications, health-related quality of life and healthcare utilisation will be based on evidence from the literature, The analysis will adopt an NHS and Personal Social Services perspective. The analysis will simulate health outcomes and health care costs over the lifetime with costs and health-related quality of life discounted at 3.5%.

6. Process Evaluation

A process evaluation will be conducted to understand what works, how does it work, for whom, in what contexts, and why. We will adopt a mixed-methods convergent parallel design, whereby quantitative and qualitative research methods will be employed simultaneously.

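### The primary model omits one randomisation stratifier (weight-loss medication use) and enters the other (WLP) only as a main effect, so the balance from stratification is not credited to 12-month weight change

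*Protocol*

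**What the plan says.** Section 3.1 of the protocol describes "1:1 allocation stratified by weight loss programme and weight loss medication usage". Section 3.4 gives the mechanics: allocation "using block randomisation (block size 6) stratified by weight loss programme" (five programmes) and by medication use in three levels. These are under 3 months of use, 3 months or more, and "no weight loss medication use over the past 6 months". That makes 15 strata.

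Section 3.5.1 sets the primary outcome as change in weight from baseline to 12 months. Section 5.2 estimates it from a "2-level mixed effects model, using weight measurements at baseline, 6 and 12 months" and names the terms: "The model will include timepoint, intervention-by-timepoint interaction, gender and WLP as fixed effects", with random intercepts for participants. Medication use is not among them. In section 5.2 WLP meets timepoint only in the separate three-way model used to look for differences in effect between programmes.

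**The concern.** An analysis should normally condition on the factors that the randomisation was constrained on. Blocking within strata forces the arms to be alike on those factors, which reduces the true sampling variability of the treatment contrast. If the factors predict the outcome and the model leaves them out, their variance stays in the residual. The model then reports a larger standard error than the design achieves.

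Two features bring this about here. One stratifier, medication use, is missing altogether, although gender, which is not a stratifier, is included. The other, WLP, is included in a form that hardly touches the primary contrast. At stake are the width of the primary confidence interval and the calibration of the primary test. The validity of the estimate is not in question.

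**Working it through.** **1. The plan's own figure.** Inputs from section 5.1: SD 22 kg, correlation 0.967, N = 1,840, 30% attrition, two-sided 5%.

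- Residual variance = 22² x (1 - 0.967²) = 31.4, so residual SD = 5.605 kg.
- Completers per arm = 1,840 x 0.7 / 2 = 644.
- SE = 5.605 x sqrt(2/644) = 0.312 kg.
- Power for 1.01 kg = Phi(1.01/0.312 - 1.96) = 89.9%. The difference detectable with 90% power is 1.0125 kg.

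The stated 90% reproduces.

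**2. Why a WLP main effect does not adjust the contrast.** Baseline, 6-month and 12-month weights are all outcomes. A WLP main effect adds the same constant to all three, so it drops out of the difference between 12 months and baseline, up to small effects of weighting. Only a stratifier x timepoint term lets the strata differ in change.

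This was checked by simulating the random-intercept model with 15 strata and blocks of 6 (500 runs, 1,290 completers, change SD 5.65 kg, correlation 0.965). The strata were assumed to explain about 11% of the variance of change.

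| Terms for the stratifiers | Mean model SE (kg) |
|---|---|
| none | 0.2544 |
| WLP main effect | 0.2545 |
| WLP and medication main effects | 0.2546 |
| WLP x timepoint | 0.2510 |
| WLP x timepoint and medication x timepoint | 0.2433 |

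The WLP main effect moved the 12-month estimate by 0.002 kg on average. Adding a medication main effect changed nothing. The two timepoint interactions lowered the model SE by 1 - 0.2433/0.2545 = 4.4%. The empirical SD of the estimate was about 0.288 under every model: the stratified design had already delivered the balance, and the interactions only let the model recognise it.

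Only the comparison between rows should be read from this table. All model SEs lie below 0.288 because the simulation let variance grow over time, which a random intercept does not capture. That is a separate matter.

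**3. Size over a range.** The documents do not say how much of the 12-month variance the strata explain, so the share R² is an assumption. It is taken out of the stated 31.4, and the model's variance is otherwise taken as correct.

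- Reported SE with strata omitted = 0.312; true SE = 0.312 x sqrt(1 - R²).
- True alpha = 2 x [1 - Phi(1.96 / sqrt(1 - R²))].
- Power, strata omitted = Phi((1.01 - 1.96 x 0.312) / true SE).
- Power, strata adjusted = Phi(1.01 / true SE - 1.96).
- Narrowing of the interval = 1 - sqrt(1 - R²).

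| Assumed R² | True SE | True alpha, omitted | Power, omitted | Power, adjusted | Interval narrower by |
|---|---|---|---|---|---|
| 2% | 0.309 | 0.0477 | 90.1% | 90.4% | 1.0% |
| 5% | 0.304 | 0.0443 | 90.4% | 91.3% | 2.5% |
| 10% | 0.296 | 0.0388 | 91.0% | 92.6% | 5.1% |
| 20% | 0.279 | 0.0284 | 92.3% | 95.1% | 10.6% |

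**The case against.** The strongest reply is that nothing breaks. The omission does not bias the estimate, the error is on the conservative side, and the planned power is kept in every row of the table. A full statistical analysis plan is promised and could add the terms. All of this is fair and limits the severity. It does not remove the point: section 5.2 names the model's terms, and an analysis plan that follows it inherits the omission.

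A reader might infer more than the documents support:

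- **That power falls below 90%.** Suppose 20% are medication users whose 12-month change differs by 6 kg. Adding 0.2 x 0.8 x 6² = 5.76 on top of 31.4 gives an SE of 0.340 and about 84% power. That calculation ignores the gain from balance; crediting it gives 86.5%. It also treats 0.967 as a correlation already net of medication use. Section 5.1 presents it as an overall baseline-to-follow-up correlation and describes no stratum adjustment, so the natural reading splits the stated variance. The 20% and 6 kg are not in the protocol either.
- **That the effect cannot be reported by medication stratum.** The stratum is recorded at randomisation, and Table 2 collects medication use at every assessment. Section 2.2 also plans moderation by the intervention used to lose weight, which may cover medication.
- **That the Study Summary commits the trial to a medication subgroup effect.** The question there is "How can SWiM be adapted for people using GLP1-RA pharmacotherapy or bariatric surgery". It concerns adapting the programme, and section 3.2 excludes previous or planned bariatric surgery, so it is not a subgroup question within this trial.
- **That gender also needs a timepoint interaction.** Gender is not a stratifier, so the randomisation argument does not reach it.

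**Conclusion.** The point holds as a modest matter of efficiency and calibration. The primary model does not condition, in any form that affects 12-month change, on either factor used to stratify the randomisation. Taken alone, this makes the reported SE too large and the test conservative. For strata explaining 2% to 20% of the residual variance, true alpha is about 0.048 to 0.028, and power for 1.01 kg is about 90% to 92% where 90% to 95% was available. The range rests on the assumed R² and on the model's variance structure being otherwise right. The sample-size statement is unaffected. It should be fixed, because the remedy is close to free and needs to be prespecified, but the primary result would not be invalid without it.

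**What to change.** In section 5.2, and in the statistical analysis plan, add the medication stratum x timepoint and WLP x timepoint terms, with their main effects, to the primary model. An equivalent is a model of 12-month weight adjusted for baseline weight and both stratifiers. Adding medication use as a main effect only would not repair the problem.

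The cost is a change of wording. Both variables are already held from randomisation. The mixed model gains 2 (medication) + 2 x 2 (medication x two follow-up visits) + 4 x 2 (WLP x two follow-up visits) = 14 parameters, against 1,840 x 0.7 = 1,288 expected completers. An intervention x medication x timepoint model alongside the planned WLP one is optional.
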